9.3 POPULATIONS FOR ANALYSES

Intention-to-Treat (ITT) Analysis Population (i.e., all randomized participants)

9.4 STATISTICAL ANALYSES

9.4.1 GENERAL APPROACH

We will convert opioids to milligram morphine equivalents (MME) using formulas published by the CDC.²⁹ Descriptive and inferential statistics will be carried out in STATA (Version 14.0; Stata Corporation, College Station, TX). The *cmp* command in STATA will be used to compute a difference in differences estimator within a mixed-model censored linear regression.³⁰ The difference in differences estimator compares the average change over time in MME dispensed for prescribers in the group receiving letter version A, compared to the average change over time for those prescribers in receiving version B. To ensure normally distributed data, we evaluate the natural log of MME. Censored regression has a continuous component and a discrete one. The natural log MME doses estimated over days where opioids were dispensed in the name of a prescriber represent the continuous part, and days with no opioids filled in that prescriber's

name represent the discrete part of the model. We denote estimation of the dependent variable as $\log(\widehat{MME})$ * to distinguish it from uncensored estimation. The analysis is represented by:

$$\log(\widehat{MME}) *_{ijk} = \beta_1 x_{1ij} + \beta_2 x_{2ij} + \beta_3 x_{3ij} + \delta_{i(k)} \quad [1]$$

where β_1 , β_2 and β_3 are fixed effects coefficients on time, x_1 , intervention, x_2 , and time by intervention interaction, x_3 , respectively. Alphabetic subscripts describe the i th prescriber, j th prescription filled and k th decedent, the nested random intercept $\delta_{i(k)}$ is normally distributed with mean zero and variance, $\sigma_{i(k)}^2$, for each i prescriber nested in (i.e., having prescribed to) decedent k , $i(k)$. With natural log transformed data, the value $100 \cdot [\exp\{\beta_3\} - 1]$ measures precisely the percentage change in MME attributable to the intervention when data are uncensored (see Woolridge (2008), pp. 212 and 410).

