8 STUDY ASSESSMENTS AND PROCEDURES

8.1 ENDPOINT AND OTHER NON-SAFETY ASSESSMENTS

Data will be obtained by providing CURES with a list of prescriber names, alongside randomized digit IDs to anonymize human subjects. The list will include the date range for retrieving all schedule II, III, and IV drugs written by the prescriber in that time. These dates will be based on the decedent date of death and letter sent date for each prescriber - 12 months before the decedent date of death and 13 months after the letter was sent, which includes a one-month wash out period. Based on the earliest decedent date of death and latest letter sent date, we will obtain data from October 1, 2017 to August 31, 2021. CURES will provide the data to USC researchers with the randomized digit IDs (i.e., omitting prescriber and patient names) to ensure the confidentiality and privacy of human subjects. All data will be transferred and reintegrated into LA Medical Examiner-Coroner's database using Secure File Transfer Protocol.

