9.2 SAMPLE SIZE DETERMINATION

We calculated the sample size needed to detect an effect of the letter intervention using standard formulas for power analysis in cluster randomized trials and the 'clusterPower' package in R statistical computing language. For this calculation we used data on decedents and prescribers at the San Diego County Medical Examiner between January 1 and December 31, 2013 published in Lev et al. 2016 and Doctor et al. 2018. We assume a two tailed test with a 5% Type I error rate and an 80% chance to detect an effect. Doctor et al. (2018) found mean of 5.5 prescribers for each decedent. Coefficient of variation we assume to be 1.22, which implies that 99% of decedents had 20 or fewer prescribers in the year before their death. We assume a 50% reduction in mean difference as compared to the effect reported in Doctor et al. 2018 and a standard deviation of +140 daily MME within cluster. Most clinician clusters for process measures have intracluster correlations that fall between 0.05 and 0.15. We assume a more conservative intracluster correlation of 0.2; in our design we randomized by decedent to reduce intracluster correlation. We utilized the Taylor method for calculating variance inflation due to unequal cluster sizes. Under these assumptions, we would need 103 decedents per study arm; given annual opioid overdose frequency in Los Angeles, we expect to have 192 per arm. We have ample power to detect an effect.

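### The primary model uses neither baseline adjustment nor the randomisation strata; adjusting is cheap and in large samples cannot lose precision, but the gain may be only about 1%

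*Combined protocol and SAP*

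**What the plan says.** Section 9.4.1 uses a Stata command "to compute a difference in differences estimator within a mixed-model censored linear regression". "The difference in differences estimator compares the average change over time in MME dispensed" for prescribers sent Letter A with the same change for those sent Letter B. Model [1] has fixed effects for time, arm and their interaction. It has one random term, "the nested random intercept" for prescriber within decedent. The interaction coefficient on log MME carries the effect. The model contains no baseline covariate, no constraint that the arms share a baseline mean, and no randomisation strata.

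Section 9.4.2, on the primary endpoint, has a title but no text, so section 9.4.1 is the only description of the primary analysis. Section 8.1 sets the data window as "12 months before the decedent date of death and 13 months after the letter was sent, which includes a one-month wash out period". Sections 4.1 and 6.3 randomise decedent clusters to the two letters, using two crossed stratification factors that give six groups.

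**The concern.** In balanced, uncensored data the interaction coefficient in model [1] is the difference between arms in mean change. It therefore subtracts the whole observed baseline difference between arms. With randomised arms that difference is chance. Subtracting all of it is optimal only when follow-up regresses on baseline with slope 1; otherwise part of what is subtracted is noise.

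What is at stake is precision, not bias. Both arms receive a letter, and section 9.2 plans on a smaller effect than the earlier trial's: "We assume a 50% reduction in mean difference as compared to the effect reported in" that trial, which compared a letter with a control group. The baseline data are already being obtained, so precision left unused here is lost for no saving. Leaving out the factors that restricted the randomisation is a second, smaller loss of the same kind.

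**Working it through.** **The plan's own figure.** The documents give no standard error and no pre-post correlation. The nearest figure is 103 decedents per arm (section 9.2), which makes no use of the baseline. Section 9.2 does not state the effect in MME. If it is half of the 6.9 in section 2.1, then delta = 3.45, and with SD 140 the unclustered size is 2 × (1.960 + 0.842)² × 140² / 3.45² = 25,850 prescribers per arm. The Taylor method with mean cluster size 5.5, CV 1.22 and ICC 0.2 gives a design effect of 1.90 / 0.637 = 2.98, so 25,850 × 2.98 / 5.5 is about 14,000 decedents per arm. The 103 is not reproduced on this reading. That is a separate matter, and baseline adjustment would not repair it.

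**Formula.** Let Y0 and Y1 be a prescriber's mean before and after the letter, with common variance s² and correlation rho. An estimator that subtracts b times the baseline difference has variance proportional to s²(1 + b² − 2b·rho).
- Difference in differences, b = 1: 2s²(1 − rho).
- Baseline-adjusted, b = rho (the minimum): s²(1 − rho²).
- Variance ratio: (1 + rho)/2. Standard error ratio: sqrt((1 + rho)/2).

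| assumed rho | SE ratio | reduction |
|---|---|---|
| 0.99 | 0.998 | 0.2% |
| 0.95 | 0.987 | 1.3% |
| 0.9 | 0.975 | 2.5% |
| 0.8 | 0.949 | 5.1% |
| 0.5 | 0.866 | 13.4% |

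A clustered simulation with an uncensored linear outcome (2 × 192 clusters, mean size about 5.5, ICC 0.2) gave ratios of 0.862, 0.917, 0.965 and 0.981 at rho 0.5, 0.7, 0.9 and 0.95. The formula gives 0.866, 0.922, 0.975 and 0.987.

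**Unequal variances.** If the follow-up SD is k times the baseline SD, the variance ratio is k²(1 − rho²)/(1 + k² − 2k·rho). It never exceeds 1, and it equals 1 when k·rho = 1. For example, k = 1.25 and rho = 0.8 give 0.5625/0.5625.

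**What rho could be.** Under model [1]'s own structure, daily residuals are independent around a fixed prescriber level. With daily within-prescriber correlation w and 365 days per period, rho = 365w/(1 + 364w). Assumed w of 0.05, 0.1, 0.2 and 0.5 give rho 0.950, 0.976, 0.989 and 0.997, and SE ratios 0.988, 0.994, 0.997 and 0.999.

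Rho is lower if prescribers drift between periods. By the schedule in section 1.3, a letter sent 1 to 6 months after death puts the window midpoints 6 + 1 + 7 = 14 to 6 + 6 + 7 = 19 months apart, so drift is plausible. As an illustration, assume prescriber variance 1, daily residual variance 3 and a prescriber-by-period variance v. Then rho = 1/(1 + v + 3/365). For v = 0, 0.05, 0.1 and 0.3, rho is 0.992, 0.945, 0.902 and 0.764, and the SE ratio is 0.998, 0.986, 0.975 and 0.939.

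Rho cannot be recovered from the earlier trial's table in section 2.1. Its interval for the letter arm's change is just the difference of opposite interval ends (63.8 − 73.7 = −9.9; 67.5 − 71.3 = −3.8), so it carries no information on correlation.

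**Printed against true standard error.** Take v = 0.1 and 192 × 5.5 = 1,056 independent prescribers per arm.
- True, difference in differences: sqrt(4 × (0.1 + 3/365)/1,056) = 0.0202.
- True, baseline-adjusted: sqrt(2 × 1.108 × (1 − 0.902²)/1,056) = 0.0197.
- Printed by model [1], with v absorbed into the daily residual: about sqrt(4 × 3.1/(365 × 1,056)) = 0.0057.

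Without a prescriber-by-period term the model treats a year's mean as almost error-free. Its implied baseline weight is about 1/(1 + 3.1/365) = 0.99 against an optimum of 0.90, so constraining the baseline means alone would gain little.

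**The case against.** The strongest reply is that this is a preference. Difference in differences is unbiased under randomisation, matches the endpoint as worded in section 3 (average change over time), and keeps the form in which section 2.1 reports the earlier randomised trial. All of that stands, except that the endpoint wording does not require this estimator. Under randomisation the arms share an expected baseline, so the difference in mean change and the baseline-adjusted difference target the same quantity.

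A second reply is that a long baseline works against a large gain, because averaging 12 months pushes rho up. This also stands, and it limits the size of the point.

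A reader might infer three stronger things that the documents do not support.
- **That the contrast is a raw subtraction of means, or an error.** It is estimated inside a mixed censored model with a prescriber intercept, and it is valid.
- **That adjustment is worth tens of decedents per arm.** At 192 per arm, 192/0.75 = 256 (64 extra) needs rho = 0.5. At rho 0.95 the figure is 192/0.975 = 197 (5 extra), and at 0.99 it is 193 (1 extra). Nothing in the documents selects among these.
- **That the reported standard error will fall.** If prescribers drift, model [1] prints too small a value, and a correct model will print a larger one.

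**Conclusion.** The point holds as an efficiency improvement. The planned estimator is valid but does not make the best use of a baseline that is already collected, and it ignores the strata used in randomisation. In large samples, for a linear outcome, baseline adjustment cannot raise the true standard error.

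The reduction is about 1% or less if model [1]'s structure is right, 2.5% at rho 0.9, and about 5% or more only if rho is 0.8 or lower. These sizes assume equal variances and an uncensored outcome, and they are approximate for the censored log model. Rho, the daily correlations and the variance components are all assumptions. The gain from the strata is not quantified, because the documents do not say how much variation they explain.

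**What to change.** Before outcomes are seen by arm, fill in section 9.4.2 with one primary model:

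- the same mixed censored model with the baseline arm means constrained equal (drop the arm main effect, keep time and time-by-arm), plus a prescriber-by-period random term, so that the model can gain from the baseline and its printed standard error is honest; or
- a model of the post-letter period adjusted for each prescriber's baseline log MME, with an indicator for no baseline opioid dispensing.

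The indicator is needed because section 5.1 admits prescribers of any schedule II to IV drug and section 4.1 has a benzodiazepine-only category. Log baseline MME can therefore be undefined for some members of the intention-to-treat population in section 9.3. The constrained-means model avoids this.

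In either model, add the six strata of section 4.1 as covariates. Section 6.3 speaks of two lists, so first confirm which scheme is used. Report the pre-post correlation, and keep the difference in differences as a sensitivity analysis for comparison with the earlier trial.

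The cost is a paragraph of analysis text and a slightly more complex model. The downside is a primary estimator that differs in form from the earlier trial's, which the sensitivity analysis covers. No new data are needed.

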4 STUDY DESIGN

4.1 OVERALL DESIGN

This is a decedent-cluster randomized field experiment; clusters of prescribers within each decedent will be randomly allocated to one of two letters interventions. This design avoids treatment contamination—clinicians prescribing to the same patient will be able to share information about the intervention without diluting its effect. If two or more decedents have the same prescriber, that prescriber will be assigned to one and only one of those decedent clusters by random draw. Two factors will serve as random strata: 1) whether the decedent received a prescription from a clinician with a single or multiple deaths, and 2) whether opioids only, opioids in combination with benzodiazepines, or benzodiazepines only were the cause of death. The first strata are designed to form equivalent groups on prescriber risk posture. The second strata equate preference for type of scheduled drug prescribed in practice. Strata will be crossed to form $2 \times 3 = 6$ randomization groups.

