6.3 MEASURES TO MINIMIZE BIAS: RANDOMIZATION AND BLINDING

For randomization, two decedent lists will be generated from the crossed strata levels. Using random.org’s sequence generator, two true random integer sequences derived from atmospheric noise will determine decedent order in each list. For each ordered list, prescribers to decedents in the first half will receive Letter A, the second half of the list will receive Letter B.

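### Equation [1] tests a pre-to-post change with only a time-constant random intercept and no decedent-clustered variance, so its standard error is too small whenever true changes vary between prescribers

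*Combined protocol and SAP*

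**What the plan says.** Section 4.1 makes the decedent the unit of randomisation: "clusters of prescribers within each decedent will be randomly allocated to one of two letters interventions". A prescriber linked to several decedents is placed in a single cluster: "that prescriber will be assigned to one and only one of those decedent clusters by random draw". Section 6.3 allocates by position in the ordered decedent list: "prescribers to decedents in the first half will receive Letter A, the second half of the list will receive Letter B".

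Section 9.4.1 defines the comparison: "The difference in differences estimator compares the average change over time in MME dispensed for prescribers in the group receiving letter version A", against the same quantity for version B. The tested coefficient is β3, the time-by-intervention term of equation [1]. The one random term, in the equation and in the text, is a normally distributed intercept for each "prescriber nested in (i.e., having prescribed to) decedent".

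Section 9.2 sets the error rates, "We assume a two tailed test with a 5% Type I error rate and an 80% chance to detect an effect", and allows for clustering at the design stage with an intracluster correlation of 0.2: "We utilized the Taylor method for calculating variance inflation due to unequal cluster sizes".

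Section 9.4.2, where the primary analysis would be detailed, has no content. No section names a random period effect, a cluster-robust variance, a bootstrap or a permutation test.

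**The concern.** β3 contrasts changes, and the letters are assigned to decedents. Its standard error must therefore reflect how much true changes differ from prescriber to prescriber, and how alike they are among prescribers to one decedent. Equation [1] has no term for either. Its intercept absorbs differences in prescribing level, and level drops out of a before-after difference. If inference rests on the model's own standard error, each extra day of data shrinks that error as though every prescriber in an arm had changed by the same amount.

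The protocol does not expect equal changes. Section 3 sets out to find factors that predict who responds, and sections 8.2 and 9.4.4 count individual prescribers whose prescribing falls by more than 20%. There are also reasons for changes to be correlated within a decedent. Section 4.1 foresees that clinicians treating the same patient will talk to each other. Section 8.1 anchors the data window to the date of death, with data from October 2017. The earliest baselines therefore precede the October 2018 CURES requirement cited in the letters, and the later ones follow it.

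At stake are the confidence interval and the 5% error rate of the only randomised comparison.

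**Working it through.** **What the plan's own figures offer.** The plan states no standard error or design effect for β3, so there is none to reproduce. The 103 decedents per arm in 9.2 does not reproduce with 140 as an SD: with half of the earlier trial's 6.9 MME (3.45) and a Taylor design effect of 2.98, 2 × 140² × 7.849 / 3.45² × 2.98 / 5.5 gives about 14,000. With 140 as a variance it gives about 100. That is a separate matter and does not enter below.

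**Inputs.** From the documents: 192 decedents expected per arm, mean 5.5 prescribers per decedent, cluster-size CV 1.22 and ICC 0.2 (9.2); 12 months before and after (1.1). Assumed, because the documents are silent: τ, the SD of true pre-to-post change in log MME; the ICC of that change; s, the residual SD of daily log MME; n, days per period. Section 9.2 does not say whether its 0.2 refers to level or to change, so the ICC of change is taken from 0 to 0.2.

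**Step 1: variance of a change.** With balanced, uncensored data the intercept cancels. One prescriber's observed change has variance τ² + 2s²/n; the model recognises only 2s²/n. With decedent correlation, τ² is multiplied by a design effect DE. The ratio of true to model variance is

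R = 1 + τ² × DE × n / (2s²), and type I error = 2 × [1 − Φ(1.96/√R)].

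DE = 1 at ICC 0. At ICC 0.2, with prescribers weighted equally, DE = 1 + ((1.22² + 1) × 5.5 − 1) × 0.2 = 3.537.

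**Step 2: numbers.** For τ = 0.10, s = 1, n = 365, DE = 3.537: R = 1 + 0.01 × 3.537 × 182.5 = 7.455, 1.96/√R = 0.718, type I error 47%.

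| s, n | τ = 0.05 (ICC 0 to 0.2) | τ = 0.10 (ICC 0 to 0.2) |
|---|---|---|
| 1, 365 | 10.4% to 22.5% | 24.4% to 47.3% |
| 2, 365 | 6% to 10% | 10% to 23% |
| 2, 100 | 5.4% to 6.3% | 6.5% to 10.3% |

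At τ = 0 every entry is 5%. For scale, τ = 0.10 puts about 95% of true changes between exp(−0.196) = 0.82 and exp(0.196) = 1.22 times the arm average. At τ = 0.20 the mildest row (s = 2, n = 100) gives 11% to 24%.

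**Step 3: uncensored simulation.** No true effect, 192 decedents per arm, s = 1, 2,000 runs per setting.

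| Days per period | τ | ICC of change | Model SE | Decedent-clustered SE |
|---|---|---|---|---|
| 365 | 0 | 0 | 5.3% | 5.5% |
| 365 | 0.10 | 0 | 24.6% | 4.9% |
| 365 | 0.10 | 0.2 | 44.6% | 5.3% |
| 100 | 0.10 | 0 | 10.3% | 4.4% |
| 100 | 0.10 | 0.2 | 24.0% | 5.9% |

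**Step 4: censored simulation.** A Tobit model with a normal prescriber intercept, about 40% of days censored, about 2,110 prescribers, 800 replicates per setting (Monte Carlo SE 0.8 points at 5%). With s = 1 and 365 days, type I error using the model SE was 4.6% at τ = 0, 8.0% (ICC 0) to 17.6% (ICC 0.2) at τ = 0.05, and 23.4% to 41.8% at τ = 0.10. With s = 2, 100 days and ICC 0.2 it was 7.4% at τ = 0.05 and 9.4% at τ = 0.10. The decedent-clustered SE gave 4.9–6.2% in all seven settings. At τ = 0.10 and ICC 0.2 (s = 1, 365 days) the model SE was 0.0036, the empirical SD of β3 0.0089 and the clustered SE 0.0088.

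**Step 5: would a decedent intercept help?** If the nested term is read as also supplying a decedent intercept, that too is constant in time. Adding one in a small uncensored fit left the SE at 0.03178 against 0.03178.

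**The case against.** The strongest reply is that this is an omission and not a stated wrong method. Equation [1] is schematic: it shows no residual term, and the plan never says that model-based standard errors will be used. An analyst could cluster by decedent without departing from it. That is true, and the conclusion is conditional on the model's own SE being used. But the stated model leads there by default, and leaving the choice open makes significance depend on an unstated option.

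The size is assumed throughout, and the highest figures come from the least favourable combination (s = 1, 365 days). This stands. With s = 2 and 100 days the inflation at τ = 0.05 is negligible, and heavier censoring would soften it: an approximate scaling to 90% censored days, with s = 1, gives 7–12% at τ = 0.05. Larger τ pushes every figure back up.

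Decedent correlation is also not an independent trigger. If true changes do not vary there is nothing to correlate, so the operative condition is τ above zero.

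Finally, the documents do not show that the planned command offers a clustered variance for this hierarchical censored model, and 9.4.1 writes no model for benzodiazepine equivalents. Both limit how the remedy can be worded; neither touches the mechanism.

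**Conclusion.** The concern holds. With the variance structure written in 9.4.1, the standard error of β3 is right only if all prescribers in an arm share one true change and days are independent given the intercept. Otherwise intervals are too narrow and the type I error exceeds 5%.

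How far it exceeds 5% cannot be settled from the documents. Over the assumptions tabulated (τ of 0.05 to 0.10, ICC of change 0 to 0.2), it runs from barely above 5% to 47%. The cancellation is exact for balanced uncensored data and approximate under censoring; the censored simulation shows that censoring does not remove the problem. Because this is the trial's only randomised comparison and the protocol itself expects unequal responses, the variance method should be fixed before the analysis is run.

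**What to change.** In 9.4.1, keep the point estimator and add a sentence stating that standard errors, intervals and tests for β3 use variance clustered by decedent, and that the same holds for the benzodiazepine endpoint under whatever model is specified for it. This is workable because 4.1 places each prescriber in exactly one decedent cluster and 2 × 192 = 384 clusters are expected. If the software does not offer it for this model, name a decedent-level permutation test that follows the randomisation, or add random period effects at both prescriber and decedent level. Adding only a decedent intercept would not help.

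The cost is one sentence and, where available, one software setting. If true changes do not vary, almost nothing is lost: the clustered SE was 1.0 times the model SE at τ = 0. If they do vary, intervals widen to their correct width, up to 2.4 times in the censored simulation (0.0088/0.0036), and the power claim in 9.2 should be reread in that light.
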